### **8.2.3. Electrocardiograms**

- Triplicate 12-lead ECG will be obtained as outlined in the SoA (see Section 1.3) using an ECG machine that automatically calculates the heart rate and measures PR, QRS, QT, and QTc intervals. Refer to Section 7 for QTc withdrawal criteria and additional QTc readings that may be necessary.
- At Screening where a triplicate ECG are required, 3 individual ECG tracings should be obtained as closely as possible in succession, but no more than 2 minutes apart. The full set of triplicates should be completed in less than 4 minutes.

### **8.2.4. Clinical Safety Laboratory Assessments**

Refer to [Appendix 2](#) for the list of clinical laboratory tests to be performed and to the SoA for the timing and frequency.

- The investigator must review the laboratory report, document this review, and record any clinically relevant changes occurring during the study in the AE section of the CRF. The laboratory reports must be filed with the source documents.
- All laboratory tests with values considered clinically significantly abnormal during participation in the study or within one day after the last administration of study intervention should be repeated until the values return to normal or baseline or are no longer considered significantly abnormal by the investigator or medical monitor.

- If such values do not return to normal/baseline within a period of time judged reasonable by the investigator, the etiology should be identified and the sponsor notified.
- All protocol-required laboratory assessments, as defined in [Appendix 2](#), must be conducted in accordance with the laboratory manual and the SoA.

### **8.2.5. Pregnancy Testing**

- Refer to Section [5.1](#) Inclusion Criteria for pregnancy testing entry criteria.
- Pregnancy testing (urine or serum as required by local regulations) should be conducted prior to each challenge during the study intervention period.
- Pregnancy testing (urine or serum as required by local regulations) should be conducted at the end of relevant systemic exposure.
- Additional serum or urine pregnancy tests may be performed, as determined necessary by the investigator or required by local regulation, to establish the absence of pregnancy at any time during the participant's participation in the study.

## **8.3. Adverse Events and Serious Adverse Events**

The definitions of an AE or SAE can be found in [Appendix 3](#).

AEs will be reported by the participant (or, when appropriate, by a caregiver, surrogate, or the participant's legally authorized representative).

The investigator and any qualified designees are responsible for detecting, documenting, and reporting events that meet the definition of an AE or SAE and remain responsible for following up AEs that are serious, considered related to the study intervention or the study, or that caused the participant to discontinue the study (see Section [7](#)).

### **8.3.1. Time Period and Frequency for Collecting AE and SAE Information**

- All SAEs will be collected from the signing of the informed consent form until 2 hrs after the last SP challenge, as specified in the SoA (Section [1.3](#)).
- All AEs will be collected from the first challenge-related procedure until 2 hrs after the last SP challenge, as specified in the SoA (Section [1.3](#)).
- Medical occurrences that begin before the start of study intervention but after obtaining informed consent will be recorded on the Medical History/Current Medical Conditions section of the case report form (CRF) not the AE section.
- All SAEs will be recorded and reported to the sponsor or designee immediately and under no circumstance should this exceed 24 hours, as indicated in [Appendix 3](#). The investigator will submit any updated SAE data to the sponsor within 24 hours of it being available.

- Investigators are not obligated to actively seek AEs or SAEs after the conclusion of the study participation. However, if the investigator learns of any SAE, including a death, at any time after a participant has been discharged from the study, and he/she considers the event to be reasonably related to the study intervention or study participation, the investigator must promptly notify the sponsor.

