### Number of Participants:

Part 1 will enrol a sufficient number of participants to achieve up to 12 participants who have completed the challenge visit. Once Part 1 is complete, SP concentrations to be given in Part 2 will be confirmed. Part 2 will occur only if Part 1 is successful.

Part 2 will enrol a sufficient number of participants to achieve up to 20 participants who have completed the 2 challenge visits. The study may be stopped after review of data from about the first 10 participants.

Participants who withdraw or are withdrawn from the study may be replaced. In Part 2, following screening, replacement participants must start at Challenge Visit 1.

Participants may be enrolled into Part 1 or Part 2, not both. Therefore, the anticipated sample size is up to 32 participants (not including replacements).

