### 1.3.2. Part 1 & Part 2 Challenge Visits

Visit (V)	V1, V2 (Part 2 only)					Follow-up phone call (5-7 days post last challenge day)	Early withdrawal	Notes
Procedure	Pre-challenge	Within 1 h before first control challenge	At least 20 min before first SP challenge	SP challenges	2 h after last SP challenge			
Clinical chemistry/Haematology and urinalysis		X			X*		X	*In Part 2, 2 h post last SP challenge at last challenge visit only.
12-lead ECG		X			X		X	Triuplicate measurements.
Vital signs		X			X		X	Refer to Section 8.2.2.
Brief PE		X						
Urine pregnancy test (WCBP only)	X							
Visual check of planned challenge sites	X							Prior to any other study procedures.
Saline and Histamine challenges			X					Histamine to be administered at least 20 cm from any IDM sampling
SP challenge				X				Part 1: Up to 4 SP injections: increasing concentrations of SP at a minimum of 20-min intervals. Part 2: Up to 10 SP injections: 

• up to 4 increasing concentrations of SP at a minimum of 20-min intervals, in duplicate

Visit (V)	V1, V2 (Part 2 only)					Follow-up phone call (5-7 days post last challenge day)	Early withdrawal	Notes
Procedure	Pre-challenge	Within 1 h before first control challenge	At least 20 min before first SP challenge	SP challenges	2 h after last SP challenge			
								
 
• a further 2 SP injections at one concentration may also be given, if ongoing data suggest biopsy samples are required
 

Wheal and flare assessment		See Section 1.3.3						
Blood sample for exploratory biomarkers		X			X			Part 2, V2 only.
IDM		See Section 1.3.3						Part 2 only
Skin punch biopsy		See Section 1.3.3						Part 2, V2 only. May or may not be performed based on ongoing data.
AE review		<===== =====>					X	
SAE review		<===== =====>					X	
Concomitant medication review		X						Review of medications since last visit, if applicable.
Follow-up on possible reactions at sites of IDM/biopsy						X		Part 2 only.

Abbreviations: AE = adverse event; ECG = electrocardiogram; IDM = intradermal microdialysis; SAE = serious adverse event; SP = substance P.

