**At each challenge visit, up to 4 concentrations of SP will be assessed, as follows:**

- In Parts 1 and 2:
  - Participants will first receive saline, by intradermal injection, and histamine by skin prick, as negative and positive controls.
  - If the wheal responses within the 20 min after each control challenge do not meet the acceptable saline and histamine responses (as defined in the SRM), the participant will not receive SP.
    - If it happens in Part 1 or on Challenge Visit 1 in Part 2, the participant will be withdrawn from the study.
    - If it happens on Challenge Visit 2 in Part 2 and if the participant marginally fails to meet the control criteria (as defined in the SRM), they may have the tests repeated. If they still fail to meet the control criteria, they will be withdrawn from the study.
  - Following confirmation of acceptable control responses, participants will receive up to 4 intradermal injections of SP at different concentrations; injections will be given sequentially from lowest to highest concentration; wheal and flare responses will be assessed after each challenge.

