## **7.3. Participant Discontinuation/Withdrawal from the Study**

- A participant may withdraw from the study at any time at his/her own request or may be withdrawn at any time at the discretion of the investigator for safety, behavioural, compliance or administrative reasons. This is expected to be uncommon.
- At the time of study discontinuation, the participant should undergo the assessments for early withdrawal shown in the SoA.
- The participant will be permanently discontinued both from the study intervention and from the study at that time.
- If the participant withdraws consent for disclosure of future information, the sponsor may retain and continue to use any data collected before such a withdrawal of consent.
- If a participant withdraws from the study, he/she may request destruction of any samples taken and not tested, and the investigator must document this in the site study records.

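### Adverse event collection closes 2 h after the last Substance P challenge, yet Part 2 follows up procedure sites by phone 5–7 days later

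*Protocol*

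**What the plan says.** Protocol 8.3.1 gives AEs and SAEs different starting points but the same end. For non-serious events: "All AEs will be collected from the first challenge-related procedure until 2 hrs after the last SP challenge". For serious events: "All SAEs will be collected from the signing of the informed consent form until 2 hrs after the last SP challenge". Both sentences refer to the SoA for the specification.

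The SoA for the challenge visits (Protocol 1.3.2) has a column for a phone call 5–7 days after the last challenge day. A Part 2 row marked in that column reads "Follow-up on possible reactions at sites of IDM/biopsy". Protocol 4.4 counts the call as part of completing the study. The skin biopsy entry in the risk table (Protocol 2.3.1) relies partly on follow-up after the participant leaves the unit.

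The SoA also marks AE and SAE review under early withdrawal, and Protocol 7.3 applies that column to everyone who leaves the study: "At the time of study discontinuation, the participant should undergo the assessments for early withdrawal shown in the SoA".

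Incidence of AEs and SAEs is a Part 2 secondary endpoint (Protocol 3, SAP 1.1). SAP 4.5.2 reports the percentage of participants with each AE, puts every non-serious AE in the disclosure table, and gives its emergent-AE definition a start but no end.

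**The concern.** In Part 2 the participant is still in the study, and is still to be asked about procedure sites, for several days after AE collection has closed. The protocol itself expects trouble at these sites. Protocol 2.3.1 names pain, bruising and irritation for IDM, and bleeding, infection and scarring for biopsy, and tells participants to check biopsy sites and report concerns. Some of these effects would not be expected to show within 2 h.

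The only rationale given for 2 h (Protocol 4.2) concerns how long wheal and flare take to resolve. It does not address IDM or biopsy sites.

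The AE definition in Appendix 3 does not depend on causality, so a late site reaction would ordinarily count. Whether it enters the incidence figure is decided by the collection window, and a window that closes too early makes the reported Part 2 incidence too low for procedure-site reactions.

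**Working it through.** The plan states no figure to reproduce. The check compares the texts and adds simple arithmetic on the gap and its possible effect.

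**Does another passage extend collection to the call?**

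- Protocol 8.3 gives the investigator a general duty to detect and report AEs but sets no period.
- Protocol 8.3.3 requires follow-up at later contacts only once an event has been reported.
- The last point of 8.3.1 requires notification of SAEs learned of after discharge and considered related. It does not cover non-serious events.
- SAP 4.5.2 has no end date but can analyse only what was collected.

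None of these brings a new non-serious event found at the call into the AE data.

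**What does the SoA arrow show?** The AE and SAE review rows contain an arrow whose right-hand end cannot be read in the text available, so both readings were followed.

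1. It stops at the column for 2 h after the last challenge. The SoA then agrees with 8.3.1, and late non-serious site reactions are outside AE collection.
2. It reaches the call. The SoA then requires AE review 5–7 days later and contradicts the 2 h limit in 8.3.1.

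**A conflict that does not depend on the arrow.** The separate mark for AE and SAE review lies under early withdrawal. A Part 2 participant may leave between the two visits, or may fail the Visit 2 controls and so receive no further Substance P (Protocol 4.1: "If they still fail to meet the control criteria, they will be withdrawn from the study"). Either would be reviewed for AEs more than 2 h after their own last challenge, outside the window in 8.3.1.

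**Length of the gap.** Counting days as 24 h from the last challenge:

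- shortest: 5 × 24 − 2 = 118 h (118/24 = 4.9 days)
- longest: 7 × 24 − 2 = 166 h (166/24 = 6.9 days)

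Counting calendar days instead, and assuming that the window closes between 12:00 and 20:00 and the call is made between 09:00 and 17:00:

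- shortest: 5 × 24 + 9 − 20 = 109 h
- longest: 7 × 24 + 17 − 12 = 173 h

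These clock times are assumptions; the documents give none.

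**Time covered after a procedure.** One biopsy is taken about 1 h after its challenge (Protocol 1.2, Figure 2, Panel C). If that challenge is the last, collection ends about 2 − 1 = 1 h after the biopsy.

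**Sites at Visit 2 among 20 completers** (sites at risk, not expected events):

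- IDM: (4 Substance P + 1 saline) × 20 = 100 at most
- biopsy, if done: 3 × 20 = 60 at most

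**Effect on incidence.** One participant whose only AE is a missed late reaction changes the Part 2 percentage by:

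- 1/20 = 5 points with 20 participants
- 1/10 = 10 points with 10 participants; Protocol 1.1 allows this: "The study may be stopped after review of data from about the first 10 participants"

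The denominator can be larger than either figure. Withdrawn participants may be replaced ("Participants who withdraw or are withdrawn from the study may be replaced"), the Safety population keeps anyone with one challenge-related procedure, and enrolment may continue during the review at about 10 (Protocol 9.5). A larger denominator makes each shift smaller.

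**The case against.** The strongest reply is that the decisive SoA cell cannot be read. Since 8.3.1 defers to the SoA, an arrow reaching the call would mean that AE review is already scheduled there; only one line of text would need aligning and the risk of understated incidence would largely disappear. That is right, and it is why the conclusion is stated as an either/or. The text needs correcting in both cases.

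A second reply is that a review at early withdrawal may pick up events that began inside the window, because the date of a review does not limit the date of onset. This has some force. But 8.3.1 ends collection itself at 2 h, and nothing says whether events that began later and are elicited at that review are to be recorded.

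A third reply is that little goes unasked. The call has its own row for site reactions, participants are told to report biopsy problems, and related SAEs have a backstop. Reactions to Visit 1 IDM that appear before the Visit 2 cut-off are collected in those given Substance P at Visit 2. All of this stands, and it confines the gap to recording. The case report form was not available, so how answers at the call are captured is unknown.

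Finally, the objective is the safety of Substance P rather than of the sampling procedures, biopsies are optional and confined to Visit 2, and safety is only described. These points limit the weight of the finding. They do not remove it, because the IDM sites receive Substance P or saline and the AE definition does not require causality.

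**Conclusion.** The concern holds. Either new non-serious site reactions arising after the 2 h cut-off fall outside AE collection in Part 2, or 8.3.1 contradicts the SoA. The early-withdrawal review sits outside the stated window on either reading.

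The importance is minor to moderate: no hypothesis test is affected, but a secondary endpoint and the disclosure table could understate procedure-site reactions. Those affected are up to 20 planned Part 2 completers, plus any withdrawn or replaced participants who had IDM, for whom no cap is set. The 5- and 10-point shifts assume denominators of exactly 20 and 10 and a participant with no other AE. How many events would be lost cannot be estimated. Confidence is medium because of the unread arrow.

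**What to change.** In Protocol 8.3.1, extend the Part 2 AE and SAE collection period to the existing follow-up call, or to the early-withdrawal assessment for those who leave early. Make the AE and SAE review rows of the SoA match, and say that reactions reported at the call are recorded as AEs.

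The emergent definition in SAP 4.5.2 would then take these events into the overall tables unchanged. Its relatedness tables cover only Substance P and histamine, so add a listing of AEs at IDM and biopsy sites; otherwise procedure events cannot be told apart from the rest.

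The cost is protocol wording, one SAP listing and minor case report form work at a call that already takes place, assuming the existing AE page can be used. The reported AE count may rise slightly, and without the listing procedure events would blur an endpoint meant to describe Substance P.

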### **8.3.2. Method of Detecting AEs and SAEs**

- The method of recording, evaluating, and assessing causality of AEs and SAEs and the procedures for completing and transmitting SAE reports are provided in [Appendix 3](#).
- Care will be taken not to introduce bias when detecting AE and/or SAE. Open-ended and non-leading verbal questioning of the participant is the preferred method to inquire about AE occurrence.

### **8.3.3. Follow-up of AEs and SAEs**

After the initial AE/SAE report, the investigator is required to proactively follow each participant at subsequent visits/contacts. All SAEs, will be followed until the event is resolved, stabilized, otherwise explained, or the participant is lost to follow-up (as defined in Section [7.4](#)). Further information on follow-up procedures is given in [Appendix 3](#).

### **8.3.4. Regulatory Reporting Requirements for SAEs**

- Prompt notification by the investigator to the sponsor of a SAE is essential so that legal obligations and ethical responsibilities towards the safety of participants and the safety of a study intervention under clinical investigation are met.
- The sponsor has a legal responsibility to notify both the local regulatory authority and other regulatory agencies about the safety of a study intervention under clinical investigation. The sponsor will comply with country-specific regulatory requirements relating to safety reporting to the regulatory authority, Institutional Review Boards (IRB)/Independent Ethics Committees (IEC), and investigators.
- An investigator who receives an investigator safety report describing a SAE or other specific safety information (e.g., summary or listing of SAEs) from the sponsor will review and then file it along with other relevant documents and will notify the IRB/IEC, if appropriate according to local requirements.

### **8.3.5. Pregnancy**

- Details of all pregnancies in female participants will be collected after the start of study intervention and until end of last challenge visit. If a pregnancy is reported, the investigator will record pregnancy information on the appropriate form and submit it to GSK within 24 hours of learning of the female participant pregnancy. While pregnancy itself is not considered to be an AE or SAE, any pregnancy complication

or elective termination of a pregnancy for medical reasons will be reported as an AE or SAE.

- Abnormal pregnancy outcomes (e.g., spontaneous abortion, fetal death, stillbirth, congenital anomalies, ectopic pregnancy) are considered SAEs and will be reported as such.
- The participant will be followed to determine the outcome of the pregnancy. The investigator will collect follow-up information on the participant and the neonate and the information will be forwarded to the sponsor.
- Any post-study pregnancy-related SAE considered reasonably related to the study intervention by the investigator will be reported to the sponsor as described in Section 8.3.4 . While the investigator is not obligated to actively seek this information in former study participants she may learn of an SAE through spontaneous reporting.
- Any female participant who becomes pregnant while participating in the study will discontinue study intervention or be withdrawn from the study.

#### **8.4. Pharmacokinetics**

Not applicable to this study.

#### **8.5. Pharmacodynamics**

##### **8.5.1. Visual check of planned challenge sites and administration of challenge agents**

At each challenge visit, before any challenge related procedures are performed, the investigator (or delegate) will visually inspect the planned challenge sites for any markings or reactions that could interfere with the interpretation of data (e.g. carryover effects from a previous challenge day).

Saline and SP will be delivered by intradermal injection and histamine will be delivered by skin prick, as described in the SRM.

##### **8.5.2. Wheal and Flare Assessments**

Callipers will be used to measure the area of the responses at the sites of saline, histamine and SP challenge. Responses will also be digitally photographed for confirmation of results. In addition, perfusion of each challenge site will be measured using laser speckle contrast imaging.

Further details are provided in the SRM.

#### **8.6. Genetics**

Not applicable to this study.

## 8.7. Biomarkers

At challenge visits defined in the SoA, the following samples will be collected to measure exploratory biomarkers:

- IDM probes will be inserted intradermally in the skin of the forearm – in total, approximately 450 µl of dialysate will be collected from each probe
- 3 punch biopsy samples of up to 3mm in diameter each will be collected
- Up to 56mL of blood will be collected via venipuncture or cannula

Details of the processing, storage and shipping procedures for all samples are provided in the SRM.

IDM samples will be collected to investigate the effect of intradermal SP challenge on local exploratory biomarkers of mast cell activation and their variability. Biomarkers may include but not be limited to histamine.

Skin biopsies may be collected to investigate the effect of intradermal SP challenge on local exploratory biomarkers of mast cell activation and their variability. Biomarkers will include tryptase and/or markers of cells including mast cells, eosinophils, basophils, T cells, macrophages and neutrophils.

Blood samples will be stored and analysis may be performed on biomarkers thought to play a role in mast cell activation or SP challenge response.

GSK may store samples for up to 15 years after the end of the study to achieve study objectives. Additionally, with participants consent, samples may be used for further research by GSK or others such as universities or other companies to contribute to the understanding of mast cell related or other diseases, the development of related or new treatments or research methods.

Exploratory biomarker results may be entered into the clinical study database or reported separately.

